Study Protocol
Study #: CRIR-1284-1217

Words on the Brain: Can Reading Rehabilitation for Age-Related Vision Impairment Improve Cognitive Functioning?

Sponsored By: Université de Montréal, School of Optometry

Financial Support Provided by:

- Fonds de la Recherche en Santé du Québec
- Canadian Institutes of Health Research (CIHR)

Principal Investigator: [name]

Co-Investigators: [name], Concordia University
 [name], Université de Montréal
 [name], Concordia University
 [name], McGill University
 [name]

Collaborators: [name]
 [name]
 [name]
 [name]
 [name]

Study Management: [name]

Document Date: February 16th 2020

Words on the Brain:
Can Reading Rehabilitation for Low Vision Improve Cognitive Functioning?

Age-related vision impairment and cognitive impairment both become more prevalent with increasing age. Research into their mechanisms has suggested that for some of these conditions (e.g., macular degeneration/glaucoma and Alzheimer's disease) there may be an underlying common cause, or they may be causally linked to a multifactorial context of frailty. Furthermore, a pressing goal of sensory-cognitive aging research is to investigate the possibility that age-related sensory deprivation may accelerate the progression of cognitive decline. For example, hearing loss in mid-life has been identified as the strongest potentially modifiable risk factor for cognitive impairment in later life. Research has demonstrated that hearing rehabilitation may have a beneficial effect on cognitive functioning insofar as improving the quality of auditory inputs may reduce cognitive demands during listening in everyday activities. While there are data to support this for hearing rehabilitation, there are no data available on whether improving visual function through low-vision rehabilitation, specifically for reading, could have a similar protective or beneficial effect on cognitive health. Given that low-vision rehabilitation has been shown most effective for enhancing reading performance, the present proposal aims to **answer the following questions:**

- Does improved reading performance (reduced cognitive demand during reading) improve cognitive (memory) functioning in older adults with age-related vision loss?
- Is this effect equally strong in individuals who have visual impairment only, compared to those with dual vision and hearing impairments?

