Pilot data from our currently funded FRQS project focusing on cognition and AMD indicate correlations between sensory and cognitive variables in the expected directions insofar as individuals with faster reading speeds demonstrated better scores on the Montreal Cognitive Assessment^{57,58}. Given the information reviewed above, the logical direction for our investigation into the functional connection between LV and cognition is to examine the possible effects of reading rehabilitation on the cognitive abilities of LV patients over time. In order to dis-entangle the effects of visual and cognitive impairments in older adults, members of this research team have adapted cognitive tests so they can be administered to individuals with low vision^{59,60}. In parallel, we are also in the process of developing a vision-screening test that can be administered to individuals with various levels of cognitive impairment^{61,62}. This investigation will guide our future research efforts into the improvement of service provision in LV rehabilitation for the purpose of increasing the independence and health of older adults living with LV.

[figure not shown]
The objectives are to:

- Evaluate cognitive functioning and memory before, and 6 and 12 months after low vision reading rehabilitation using magnification in AMD patients, compared to those with dual (vision and hearing) impairments, and age-matched controls
- Correlate participant characteristics with all cognitive outcome variables in order to identify potential mediators, moderators or confounders

Hypotheses:

- Measures of reading effort (self-report and objective reading speed) will be statistically significantly reduced after participants have received strategies and tools to facilitate reading.
- Measures of reading behaviour will be negatively correlated with measures of reading effort (e.g., participants who report less effort will read a greater amount, more frequently and for longer)
- Individuals who demonstrate reduced reading effort and improved reading behaviour will demonstrate improved scores on cognitive tests after 6 months of having received rehabilitation strategies and tools, compared to those whose reading effort remains high or whose reading behaviour remains unchanged. These beneficial effects will be maintained after 12 months.
- Reading measures correlate with cortical thickness (CT) in the visual cortex;

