Cognitive Outcome Measures: We will investigate the potential effect of reading rehabilitation on three relevant areas of cognitive function. The first will be episodic learning and memory, assessed using the Rey Auditory Verbal Learning Test (RAVLT)⁶⁹. Second, we will assess two aspects of auditory working memory: a) general auditory working memory and will be assessed using the WAIS-IV Letter Number Sequencing task⁷⁰ and b) an auditory listening span test, which will be a variant of the reading span task originally developed by Daneman and Carpenter⁷¹ (a task highly associated with reading skill). The third domain is processing speed, and will be assessed using a computerized audio-visual choice reaction time task. Lastly, we will be assessing cognitive impairment using the adapted version of the Montreal Cognitive Assessment (MoCA)^{59,72} for persons with visual impairment, should their visual impairment be too severe to administer the visual items. This measure will provide additional information regarding the participants' cognitive abilities, and help to identify possible cognitive impairment. These measures were chosen because they cover a wide range of cognitive functions, they are all **administered in the auditory domain** and thus will not be affected by a visual impairment, and have good psychometric properties. In other words, should performance on these cognitive measures improve following the vision rehabilitation program, the improvement will be attributable to the benefit of increased visual function on cognitive stimulation as opposed to merely being due to improved perception of the stimuli involved in the tests. Their administration can be **adjusted to make instructions audible** for persons with concurrent hearing loss. Moreover, they assess cognitive domains that have been shown to predict everyday function in older adults: episodic learning and memory⁷³, processing speed⁷⁴, and working memory⁷⁵. In addition, we have aimed to harmonize as many of our cognitive measures as possible with those utilized in the Canadian Longitudinal Study on Aging, in order to increase the possibilities to compare our findings to that larger data set for 30,000 Canadians for whom baseline and first follow-up data are available⁷⁶.

Reading Outcome Measures:

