The Low Vision Evaluation & Reading Intervention is delivered through rehabilitation services at the partner centers that are **regulated by the Quebec Ministry of Health**: Following Time 1 (within 3 months), participants will receive the full complement of services available and deemed suitable by their clinical staff and rehabilitation professionals of either rehabilitation centre. Both centres have a comparable service offer according to the provision of assistive devices and services regulated by the Quebec Health Insurance (RAMQ). These services are similar to those provided within the Blind Rehab Centers of the Veterans Affairs service offer in the USA^{36,37} and include but are not limited to: a full optometric exam to determine functional vision, including refraction and the prescription of appropriate near and distance glasses and optical devices. This is followed by an assessment by a low vision therapist and/or occupational therapist that will establish the client's functional priorities and rehabilitation goals. They provide hand-held optical magnification devices, electronic non-optical

magnification devices (e.g., portable or table-top closed-circuit TVs), or computer software for screen content magnification (e.g., ZoomText). All are provided free of cost for the client and with appropriate training and follow-up sessions in the home within 3 months, if required. Participants may undergo a systematic lighting assessment^{109,110} and may receive specific lighting recommendations that will improve their reading ability. In addition, clients will have access to referral services such as orientation & mobility training (for independent travel), registration for an adapted adult day centre for individuals with sensory loss¹¹¹, as well as the possibility to access psychosocial services, counsellors, social workers or other mental health professionals. The provision of assistive devices for magnification and reading is generally linked to a follow-up visit in the client's home 3 weeks after the initial rehabilitation appointment, in order to observe the use of the devices and strategies in the environment where the client lives. It is at this point that a decision is made with the client whether the devices are useful and will be assigned to the client as a permanent loan. Should additional needs emerge, the client is at liberty to contact the rehabilitation centre at any time to initiate a new service episode.

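### The intervention is a whole low vision service package that patients can re-enter at any time, so the design supports neither attributing cognitive gains to better vision nor the claim that the initial effect lasts to 12 months

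*Combined protocol and SAP*

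**What the plan says.** The first objective is to "Evaluate cognitive functioning and memory before, and 6 and 12 months after low vision reading rehabilitation using magnification in AMD patients", with dual-impaired patients and age-matched controls as comparators. The third hypothesis predicts better cognitive scores at 6 months in those whose reading effort falls and whose reading behaviour improves, and adds: "These beneficial effects will be maintained after 12 months".

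The Cognitive Outcome Measures section explains that the tests are given by ear, and concludes that if scores rise after rehabilitation, "the improvement will be attributable to the benefit of increased visual function on cognitive stimulation" rather than to easier perception of the test material.

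The section on the Low Vision Evaluation & Reading Intervention describes something wider than magnification for reading: "participants will receive the full complement of services available and deemed suitable by their clinical staff". Besides refraction, devices, training and lighting advice, it lists orientation and mobility training, "registration for an adapted adult day centre for individuals with sensory loss", and "the possibility to access psychosocial services, counsellors, social workers or other mental health professionals". It sets no end to the intervention. If further needs arise, "the client is at liberty to contact the rehabilitation centre at any time to initiate a new service episode".

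The follow-up section counts 6 and 12 months from the initial rehabilitation appointment. Statistical Analysis – Functional measures adjusts for the severity of vision and hearing loss and considers gender, age and education. It names no service variable. The Clinical Variables section does extract the type, duration and intensity of services from the chart, and says in general terms that these data may be used for statistical control.

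**The concern.** The title asks whether reading rehabilitation improves cognition. Patients may over the same months receive other services that could affect cognition or mood without any change in reading. The protocol's own background makes such routes plausible. It links mentally stimulating activity in general, with reading as one example, to lower dementia risk. It names social disengagement as a feature of both visual and cognitive impairment. It also measures depression, anxiety and stress because psychological state may influence rehabilitation outcomes.

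Two conclusions are at stake. The first is the cause of any gain: better vision for reading, or the package as a whole. The second is durability. If services can restart between the 6- and 12-month visits, an unchanged score does not show that the initial intervention had a lasting effect.

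**Working it through.** No arithmetic applies. The plan gives no uptake figure for any service, and its sample-size calculation does not bear on attribution. The check sets each planned comparison against the question it would have to answer.

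**1. What auditory testing rules out.** Patients who see better might score higher on a visual test simply because they see the items. Auditory tests close that route. They do not address other influences on the same patients between visits. Moving from *not a perception artefact* to *caused by increased visual function* skips the other services.

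**2. Patients against controls.** The Participants section recruits controls without visual impairment, and the plan describes no services for them. Patients and controls therefore differ by the whole package, and this contrast cannot isolate the reading part.

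**3. Patients against their own baseline.** The analysis section explains that services cannot be withheld and that a waiting-list group is not workable, so participants act as their own comparison. Every service received after baseline is included in the pre-post change.

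**4. Reading improvers against non-improvers (third hypothesis and exploratory avenue 1).** This comes closest to a reading-specific question. But the groups are defined by reading change after baseline, which the other services may also influence, and services are chosen for each client by clinical staff. A positive result is necessary for a reading-specific interpretation but not sufficient.

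**5. Exploratory avenue 2.** This enters reading measures as covariates and asks whether cognitive scores still improve over time across the three groups. It gives a partial look at gains that reading does not explain. It contains no service term, conditions on post-baseline reading, and is planned only if participants do not divide clearly into improvers and non-improvers.

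**6. The cognitive model.** Vision level, hearing level, gender, age and education are named. Service type, duration and intensity are extracted but appear in no stated model.

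**7. Maintenance.** Three statements combine: follow-up is timed from the first appointment, no end of service is fixed, and a new episode may start at any time. Equal scores at 6 and 12 months could come from persistence or from further service. No planned analysis separates the two. The Limitations section accepts that delivery is outside the study's control, but does not discuss parallel services or renewed episodes.

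**The case against.** The strongest reply has four parts.

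- *The attribution sentence is read out of context.* It ends by contrasting the claim with improved perception of the stimuli, so its purpose is to justify auditory tests. That purpose is sound, but the sentence also makes a positive causal statement that the tests cannot support.
- *The other services are optional.* Day centre and counselling are referrals, and new episodes follow only from new needs. This is correct. Uptake could be low and the practical effect small. It limits how much can be said about size, but does not make the attribution follow from the design.
- *The third hypothesis compares patients with equal access to services.* Confounding therefore needs uptake to differ between improvers and non-improvers. This is also correct, and no difference is shown. But services are assigned by individual suitability, so equal uptake cannot be assumed.
- *The plan already has partial safeguards.* These are avenue 2, the mood scale, the latent factor analysis and chart extraction through the 12-month follow-up. They reduce the gap. None is specified to separate the service components or to identify renewed service.

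A reader might also infer that the comparison of vision-only with dual-impaired patients is biased in favour of the latter, through hearing aids obtained during follow-up. The introduction does say that "hearing rehabilitation may have a beneficial effect on cognitive functioning". However, the documents mention no hearing-aid fitting or hearing rehabilitation for participants, and speech-in-noise and self-reported hearing measures are repeated at each visit along with the thresholds. That inference is not supported.

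**Conclusion.** The point holds as a matter of interpretation. As designed, a gain in patients would reflect the low vision service package as delivered, and stability to 12 months would be stability with continued access to services. The plan states more than this on both counts.

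No numerical size can be given, because any shift in the cognitive contrasts would rest on uptake and effect values that the documents do not contain. A reader might infer that the other services will materially distort the results. The documents do not show that; they show only that the plan could not tell if they did.

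The conclusion assumes that at least some patients use a non-reading service or open a new episode, which the plan allows but does not quantify. The study remains useful for the package effect, within the limits of a non-randomised pre-post design.

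**What to change.** Three changes, none affecting clinical services. They can go into the stage 1 pre-registered report promised under Study Design.

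1. **Cognitive Outcome Measures.** Reword the attribution to say that auditory tests rule out better perception of the test stimuli, and that any gain reflects the service package as delivered. Add that support for the third hypothesis is necessary but not sufficient for a reading-specific interpretation.
2. **Third hypothesis and follow-up analysis.** Word the 12-month prediction as *maintained with continued access to services*. Show the Time 2 to Time 3 change descriptively, by whether the chart records a new service episode in that interval.
3. **Sensitivity analysis only.** Repeat the patients-only analysis of the third hypothesis with dated chart indicators for day centre, psychosocial and mobility services. Label it as open to confounding by indication, because services follow clinical need.

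The cost is a narrower claim and a little more analysis. Chart extraction is already planned. The team should confirm that it captures dates, new episodes, and day-centre and psychosocial referrals, since the Clinical Variables section does not list these explicitly.

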required to have a diagnosis of AMD (any type), not currently be undergoing any medical treatment for their AMD (e.g., anti-VEGF injections) and must potentially benefit from a magnification intervention for the purpose of improving their ability to read. This reading intervention requirement (see description in data collection section below) will likely result in a large number of eligible participants as reading has been reported to be the number 1 complaint of individuals seeking vision rehabilitation⁶⁶. Participants need to be able to communicate in either English or French, and have a visual acuity in the better eye of 20/60 or less with best standard refraction, according to the admission criteria for eligibility for rehabilitation services in Quebec⁶⁷. DSI participants are eligible with an additional unaided pure-tone average (PTA) hearing loss across 4 frequencies (0.5, 1, 2 and 4 kHz) between 26 dB and 70 dB⁶⁸. Those with a PTA \geq 70 dB HL in their better ear are likely to have severe problems in speech communication, and will be excluded from recruitment. Based on past experience, because we will recruit participants over the phone, those with more severe degrees of hearing impairment would unlikely be recruited for the project. Progress of our pilot study^{57,58} indicates that we will be able to recruit at least 3 AMD participants per week, making the recruitment goal feasible within 18 months. Given the familiarity of the team members of working with this population, it is our experience that recruitment is most successful when we offer the choice of coming to the lab space at either rehab centre or to be visited in their home for data collection (except for the MRI sub-study, whose participants will be randomly recruited among study participants). Therefore, informed written consent will be obtained and data will be collected either in the home or the lab at the first in-person meeting, and the procedures are developed accordingly to be easily portable.

Measures: The study includes outcomes measures of vision (e.g., reading), cognition (e.g., memory) and cortical architecture (MRI sub-study), as well as potential descriptors, clinical data and co-variants (e.g., hearing, demographics, depression etc.)

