Hearing Assessment: Given that the cognitive assessment is designed in such a way that vision is not required for the administration of the testing materials, and given that the influence of **hearing** loss has been associated with the measurement of cognition^{e.g., 84} and has been identified as a risk factor for cognitive impairment²⁴, hearing ability will be assessed as part of the protocol. In order to be able to consider hearing ability and listening effort during the cognitive assessment²⁹, participants will complete a pure-tone audiogram with a portable audiometer (Maico MA41 from GénieAudio), using Radioear DD45 earphones, to establish a mean unaided decibel hearing loss (dB HL) threshold across 0.5, 1, 2, and 4 kHz in each ear. We will document the ambient sound levels during testing, using the Decibel X app by SkyPaw Co. Ltd., because testing may be conducted in participants' homes. Ambient noise levels can then be used to statistically control for potential noise effects on hearing thresholds. For individuals who experience difficulties in hearing the experimental protocol instructions, we will have a Williams Sound Pocketalker (<https://www.williamsound.com/pocketalker>) on site in order to provide personalized amplification. In addition to pure-tone audiometric thresholds, speech-in-noise thresholds will be measured using the Canadian Digit Triplet Test in either English or French⁸⁵. Participants will complete the Hearing Handicap Inventory for the Elderly (HHIE) questionnaire and three individual questions about hearing ability which assesses their perception of difficulties with activities of daily living that require hearing⁸⁶. These hearing assessments are the same as those that have been used or are planned for the Canadian Longitudinal Study on Aging (CLSA)⁸⁷, thereby allowing us to cross-reference and compare data from both studies and optimize our ability to place our intervention findings in a larger Canadian context.

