Time 2 – 6-Months and Time 3 – 12-Months Follow-Up: Six and 12 months after the initial rehabilitation appointment, the research assistant will meet with each participant (at home or in the lab, according to their preference) in order to repeat the experimental protocol, and all reading, cognitive and hearing measures will be administered each time. Throughout the period of the protocol, data from the rehabilitation chart will be extracted as it becomes available, with the final data collection concluding after the 12-month follow-up.

Statistical Analysis – Functional measures: To analyze these data, we will examine change in cognitive test scores from baseline over time using mixed-effects regression models, adjusting for level of vision and hearing impairment as fixed or random effects, and compare across sensory group (VI/DSI/Control). The analyses will include consideration of potential moderators or confounders (i.e., gender, age, education). In addition, we will calculate effect sizes, confidence intervals and Bayes Factors for main effects, interactions, and all post-hoc analysis.

When reflecting on the question of a control group we further consulted with the rehabilitation centres and discussed recruitment approaches and limitations; however, for practical and ethical reasons we are not able to withhold rehabilitation services from a possible comparison group, and waiting times are too varied across the centers and seasons of the year to allow for a waiting-list control group. As a result, we are proposing a quasi-experimental repeated-measures design with the intent to let the participants act as their own comparison across time points.

In addition, the data allow us to follow potential **exploratory avenues of analysis:**

- 1) If the recruited participants naturally divide into individuals whose reading effort was reduced and their reading activity has increased, versus those where we do not observe a change in reading behaviour, we can compare these two groups directly (e.g., while still considering their hearing status, or their gender)

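### Question 2 rests on a VI versus DSI split at 26 dB; a pre-specified hearing-threshold-by-time model in patients would add precision at almost no cost

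*Combined protocol and SAP*

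**What the plan says.** The opening list of research questions asks: "Is this effect equally strong in individuals who have visual impairment only, compared to those with dual vision and hearing impairments". Under Participants, a dual sensory impaired (DSI) patient is one who also has an "unaided pure-tone average (PTA) hearing loss across 4 frequencies (0.5, 1, 2 and 4 kHz) between 26 dB and 70 dB". By implication, a vision-impaired-only (VI) patient falls below 26 dB. Patients at or above 70 dB in the better ear "are likely to have severe problems in speech communication, and will be excluded from recruitment".

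Under Hearing Assessment, participants have an audiogram "to establish a mean unaided decibel hearing loss (dB HL) threshold across 0.5, 1, 2, and 4 kHz in each ear", so the threshold exists as a continuous value. The follow-up section adds that "all reading, cognitive and hearing measures will be administered each time".

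Under Statistical Analysis – Functional measures, change in cognitive scores is examined with mixed-effects regression. The models adjust for the severity of vision and hearing loss (as fixed or random effects) and "compare across sensory group (VI/DSI/Control". The moderators or confounders listed there are age, education and gender. The section also promises interval estimates, Bayes factors and effect sizes, including for interactions. The objectives contain a general aim to correlate participant characteristics with the cognitive outcomes in search of moderators.

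The plan calls for 150 patients and 50 controls and does not say how many of the 150 are to be VI or DSI. The only stated split is 15 and 15, in the MRI subsample.

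**The concern.** Question 2 is about moderation: does cognitive change after rehabilitation depend on hearing? The contrast named for it uses hearing only as below or above 26 dB. Within DSI, a patient at 27 dB counts the same as one at 69 dB, while patients at 25 and 27 dB count as different. If the cognitive response varies gradually with hearing, much of the information about that gradient goes unused, and more of it as the groups become more unequal. Group sizes depend on who is recruited.

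At stake is the precision of the answer. A claim that two effects are equally strong is a claim of similarity, so it is only as good as the width of the interval around the difference. The plan gives no margin or rule for such a claim.

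**Working it through.** **The plan's own figure.** Sample Size gives n = 141 for a 3x3 within-between design, effect size 0.15, alpha 0.05, power 0.95. Reading 0.15 as Cohen's f, and assuming a correlation of 0.5 between repeated measures and no sphericity correction (neither is stated):

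- noncentrality = f² × N × m / (1 − ρ) = 0.0225 × 141 × 3 / 0.5 = 19.0
- df1 = (3 − 1)(3 − 1) = 4; df2 = (141 − 3)(3 − 1) = 276
- power = 0.952; the smallest N is 140, or 141 for three equal groups

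The figure reproduces, but for the three-group-by-time interaction. It does not address VI versus DSI, so it neither supports nor refutes what follows.

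**Patients available.** With the stated loss of about 10% at each time point, taken over two follow-ups: 150 × 0.9 × 0.9 = 121.5, or about 121 patients.

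**Information kept by the split.** For a normal predictor with a linear effect, cut so that a share p lies on one side at z, the share kept is φ(z)² / [p(1 − p)]:

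- 50:50: 0.3989² / 0.25 = 0.637
- 70:30: 0.3477² / 0.21 = 0.576
- 80:20: 0.2800² / 0.16 = 0.490

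**Power.** By Fisher's z, power = Φ(√(n − 3) × atanh(r√k) − 1.96). Here k is the share kept, n = 121, and r is the correlation between PTA and cognitive change. The documents give no r, so 0.25 and 0.30 are assumed. Example with r = 0.25: √118 = 10.86. Continuous: 10.86 × 0.2554 − 1.96 = 0.81, power 0.79. At 50:50: r√k = 0.1995, 10.86 × 0.2022 − 1.96 = 0.24, power 0.59.

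| Use of hearing | Share kept | Equivalent patients (121 × share) | Power, r = 0.25 | Power, r = 0.30 |
|---|---|---|---|---|
| Continuous PTA | 1.000 | 121 | 0.79 | 0.92 |
| Split 50:50 | 0.637 | 77 | 0.59 | 0.76 |
| Split 70:30 | 0.576 | 70 | 0.55 | 0.71 |
| Split 80:20 | 0.490 | 59 | 0.48 | 0.64 |

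**Sensitivity to the PTA distribution (all inputs assumed).**

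- Simulated PTA truncated at 70 dB and cut at 26 dB, with means 20 to 45 dB and SDs 10 to 20 dB, gives losses of about 33% to 84%. Where the DSI share is between 27% and 82%, the loss is about 33% to 53%.
- Two separated groups of equal size, with means 15 and 42 dB and SDs 6 and 10: between-group variance (27/2)² = 182.25; mean within-group variance (36 + 100)/2 = 68; share kept 182.25 / 250.25 = 0.73, a loss of about 27%.
- A true step in response at 26 dB: the split loses nothing, and a straight line would be the wrong shape.

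**The case against.** The strongest reply is that hearing level is already in the model. The sentence that sets up the group comparison also adjusts for severity of hearing impairment, and the objectives foresee a search for moderators. So a reader who infers that the plan discards the audiogram goes further than the text allows. What stands against the reply is narrower. In a model of scores over time, a main effect of hearing level shifts the average score and says nothing about whether change differs by hearing. If the outcome were coded as change from baseline, the same term would bear on change. The text can be read either way and names no hearing-level-by-time term.

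A second reply is that question 2 is worded as a comparison of two groups, and VI versus DSI estimates exactly that. This stands. A slope in decibels is a different quantity, so it belongs beside the group contrast and not in its place.

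A third is that a non-significant difference need not be mistaken for equality, because confidence intervals and Bayes factors are planned. This also stands: a reader might infer that the plan would equate the two, but no passage says so. What is missing is a rule for what would count as equally strong.

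Finally, the power figures use completers only, whereas a mixed model can use partial follow-up.

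**Conclusion.** The concern holds in a limited form. The plan's named test of question 2 is a contrast between groups cut at 26 dB, a continuous threshold is available, and no term tests whether that threshold modifies change over time. Under approximate normality and linearity, the split keeps about 64% of the information at 50:50 and 49% at 80:20.

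These percentages are conditional. A reader might take a loss of 36% to 51% as a property of this trial. The documents give neither the PTA distribution, nor the VI:DSI split of the 150 patients, nor the shape of the relation. Other assumptions give from about 27% to well above 51%, or nothing for a step at 26 dB. A reader might also infer that question 2 is the least powered part of the plan. The documents do not support that: the cortical question rests on 15 participants per group, against about 121 patients here.

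This is an inexpensive gain in precision on a headline question. It is not a flaw that invalidates the planned analysis.

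**What to change.** 1. Keep the VI versus DSI contrast in cognitive change, with its confidence interval and Bayes factor, as the direct answer to question 2.
2. Pre-specify beside it a patients-only mixed model with baseline better-ear PTA (continuous, for example per 10 dB) by time, adjusted for age by time, with a spline check for non-linearity.
3. Report from that model the difference in change between two thresholds named in advance (for illustration, 20 and 45 dB), with its confidence interval.
4. Base any statement that the effect is equally strong on the intervals and Bayes factors, not on p > 0.05.
5. Say whether the outcome is the score at each visit or change from baseline, and in what form hearing level enters the main model.

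The stage 1 pre-registered report that the plan announces is the natural place for this. The cost is one extra model on data already collected, with no new visits or tests. The downside is an assumption of near-linearity, which the spline checks.
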